## Abstract

Title	A Phase II study of Sodium thiosulfate (STS) for prevention of ototoxicity in patients with locally advanced squamous cell carcinoma of head and neck (SCCHN) undergoing concurrent chemoradiation with cisplatin
Study Description	This is a phase II study to establish feasibility of using sodium thiosulfate after intravenous cisplatin in head and neck cancer patients undergoing definitive concurrent chemoradiation for prevention of ototoxicity. Hypothesis is that use of intravenous STS would be feasible and safe in patients with locally advanced SCCHN undergoing concurrent chemoradiation with cisplatin. This is a prospective clinical trial for patients getting either weekly cisplatin (40mg/m  ) or every-3-week cisplatin (100mg/m  ). A total of 16 patients will be enrolled and each subject will have baseline and post-treatment (3 months after the completion of concurrent chemoradiation) audiogram to assess hearing loss as defined by NCI CTCAE version 5.0. STS (10 g/m  for weekly cisplatin group and 20g/m  for high dose cisplatin group) will be infused 4 hours after each cisplatin infusion is completed. Feasibility will be assessed by successful completion of planned treatment, defined by completion of 5 weekly cisplatin or 2 high dose cisplatin without any extended treatment related delays more than > 7 days.
Phase of Study	Phase II Study
Investigational Products	Sodium thiosulfate (STS)
Study population	Patients with locally advanced SCCHN (oral cavity, oropharynx, hypopharynx, and larynx) eligible for definitive concurrent chemoradiation with cisplatin would be eligible for the study. Patients must be at least 18 years old at the time of enrollment. Women and persons from ethnic minority groups are encouraged to participate the study.
Primary Objective	Primary objective is to establish feasibility of intravenous STS after each dose of concurrent cisplatin in patients with locally advanced head and neck squamous cell carcinoma undergoing definitive radiotherapy.
Secondary Objectives	Secondary objectives are to 1) determine the rate of grade $\geq 2$ change of hearing impairment from baseline based on NCI CTCAE version 5.0 with use of STS after concurrent chemoradiation with cisplatin 3 months post-treatment, 2) determine the rate of tinnitus measured by PRO-CTCAE with use of STS 3 months post-treatment, 3) describe patient reported outcomes with STS measured with PRO-CTCAE for selected oral, GI, neurologic and perceptual symptoms 4) describe patient reported outcomes measured with Hearing Handicap Inventory for Adults – Screening (HHIA-S) compared to results from standard NRG Oncology head and neck trials (such as RTOG 1016).
Sample Size	A total of 16 patients are going to be enrolled.

Duration of Study Treatment	Participants may continue study treatment for up to 7 weekly doses or 3 every 21-day doses from the time of initiating treatment.
Duration of Follow up	Participants will be followed up to 3 months post-therapy from the completion of radiation.
Unique Aspects of this Study	This is the first study to evaluate the feasibility of STS in patients with locally advanced head and neck cancer undergoing concurrent chemoradiation therapy with cisplatin.

## List of Abbreviations

AE	adverse event
ALP	alkaline phosphatase
ALT	alanine aminotransferase
AST	aspartate aminotransferase
BUN	blood urea nitrogen
CBC	complete blood cell (count)
CNS	central nervous system
CR	complete response
CRF	case report form
CT	computerized tomography
CTCAE	Common Terminology Criteria for Adverse Events
CTMS	Clinical Trial Management System
DFS	disease-free survival
DLT	dose limiting toxicity
DSMC	Data and Safety Monitoring Committee
DSMP	Data and Safety Monitoring Plan
ECG/EKG	electrocardiogram
ECOG	Eastern Cooperative Oncology Group
FDA	Food and Drug Administration
FDG	Fluorodeoxyglucose
FLC	free light chain
GCP	Good Clinical Practice
GFR	glomerular filtration rate
HBeAg	hepatitis B "e" antigen
HBV	hepatitis B virus
HCV	hepatitis C virus
HDFCCC	Helen Diller Family Comprehensive Cancer Center
HIPAA	Health Insurance Portability and Accountability Act
HIV	human immunodeficiency virus
ICF	informed consent form
ICH	International Conference on Harmonization
IDS	Investigational Drug Services (UCSF)
IND	investigational new drug application
IP	investigational product
IRB	Institutional Review Board

## List of Abbreviations

IV	intravenous
LDH	lactate dehydrogenase
MRI	magnetic resonance imaging
MTD	maximum tolerated dose
NCI	National Cancer Institute
ORR	overall response rate
PD	disease progression
PK	pharmacokinetics
PO	Per os (by mouth, orally)
PR	partial response
PRC	Protocol Review Committee (UCSF)
SD	stable disease
SGOT	serum glutamic oxaloacetic transaminase
SGPT	serum glutamic pyruvic transaminase

## 1 Introduction

### 1.1 Background on Indication

Most patients with SCCHN present with locally advanced disease which requires multimodality treatment including surgery, radiotherapy and/or chemotherapy. The majority of patients are treated with concurrent chemoradiation with cisplatin and survive the intensive treatment [2]. Especially for HPV positive SCCHN which has excellent prognosis, treatment deintensification has been attempted to save these patients from long term toxicities. Disappointingly, a recent, large randomized clinical trial comparing concurrent cetuximab and cisplatin has suggested that cetuximab may lead to inferior clinical outcome compared to cisplatin [3] and cisplatin remains the standard of care for concurrent chemoradiation in these patients. Cisplatin is a widely used systemic anti-cancer agent, and its toxicities including nephrotoxicity, neuropathy and ototoxicity have been well described. Indeed, in a prospective cohort study, 63% of locally advanced SCCHN patients who were treated with concurrent chemoradiation with cisplatin developed moderate to severe (grade  $\geq 2$  change from baseline (common terminology criteria for adverse events, CTCAE v4.03) ototoxicity with average time to onset of 2.25 months [4]. Furthermore, cisplatin induced ototoxicity seems to be dose-dependent. In testicular cancer patients, every 100mg/m^2 increase in cisplatin dose resulted in a 3.2 dB impairment in the age-adjusted overall hearing threshold[5].

### 1.2 Background on the Investigational Product(s) and Associated Known Toxicities

Sodium Thiosulfate (STS) is an inorganic compound which is used widely for gold mining, water treatment, analytic chemistry, development of silver based photographic films and prints, as well as medicine. In medicine, it has been used as an antidote for cyanide poisoning, a topical treatment for certain fungal infections, and a systemic treatment for calciphylaxis in end stage renal disease patients. STS is approved by FDA for use of cyanide poisoning in conjunction with sodium nitrite. Adverse events that have been reported in medical literature include hypotension, headache, disorientation, nausea and vomiting, prolonged bleeding time, salty taste in mouth and warm sensation over body. These adverse events were not reported in the context of controlled trials or with consistent monitoring and reporting methodologies for adverse events.

In humans, rapid administration of concentrated solutions or solutions not freshly prepared, and administration of large doses of sodium thiosulfate have been associated with a higher incidence of nausea and vomiting. However, administration of 0.1 g sodium thiosulfate per pound up to a maximum of 15 g in a 10-15% solution over 10-15 minutes was associated with nausea and vomiting in 7 of 26 patients without concomitant cyanide intoxication. In a series of 11 human subjects, a single intravenous infusion of 50 mL of 50% sodium thiosulfate was associated with increases in clotting time 1-3 days after administration. However, no significant changes were observed in other hematological parameters[6].

It also has been extensively studied as a “cisplatin rescue” agent to maximize dose intensity. Cisplatin favors positively charged platinum species, which possess both antitumor and toxic activities in a low chloride environment such as the intracellular space. Following IV administration, sodium thiosulfate rapidly distributes to extracellular space and reacts with cisplatin to form a covalently bound compound [7]. In a phase 1 study, in which cisplatin 100mg/m^2 was infused with concurrent STS followed by continuous STS infusion for 2-3 hours, the pharmacokinetic properties of cisplatin including elimination rate constant, volume of distribution, or total body clearance did not change significantly [8]. In this clinical trial, reported toxicities included elevated creatinine, myelosuppression, nausea, vomiting and hypomagnesemia, which are consistent with known effects of cisplatin.

### 1.3 Rationale for the Proposed Study

As patients with HPV positive head and neck cancers have excellent clinical outcome [9], long-term treatment related toxicities such as hearing impairment can significantly impact patients' quality of life. In head and neck cancers, sodium thiosulfate delivered after intra-arterial cisplatin has shown to be associated with decreased risks of hearing loss in previous research [10, 11]. Furthermore, recent clinical trials demonstrated IV sodium thiosulfate after 6 hours of cisplatin infusion can protect pediatric cancer patients from cisplatin induced hearing impairment with an acceptable safety profile [1, 12]. One of the trials also demonstrated that there was no significant difference in oncologic outcome between the STS group and the control group in pediatric patients with hepatoblastoma when STS infusion was given 6 hours after cisplatin dose[1]. Although efficacy and safety of STS has been established in pediatric hepatoblastoma patients receiving 480mg/m^2 (cumulative dose) of single agent cisplatin, no prospective studies exist for STS in locally advanced SCCHN patients undergoing definitive chemoradiation. Once the feasibility and safety of STS infusion are deemed promising in this population based on this phase II study, the concept could be easily expanded to a larger study for definitive testing which could be conducted in the head and neck cancer population or a broader population with various cancers which utilize cisplatin-based chemotherapy in NRG Oncology, either as a stand-alone supportive care focused trial or as an adjunctive study to existing or new therapeutic clinical trials.

[figure not shown]

Figure 1. (A) Hearing loss (Brock grade  $\geq 1$ ) occurred in 33% in cisplatin-STS group and 63% in cisplatin-alone group (RR 0.52, 95% CI 0.33-0.81)  
 (B) There was no significant difference event-free survival between

### 1.4 Rationale for the Dose Selection/Regimen

Intravenous STS 10 g/m^2 or 20 g/m^2 will be administered over 1-2 hours, 4 hours after each cisplatin dose is completed, depending on weekly or high dose cisplatin regimen. In recent clinical trials in pediatric cancer patients, STS 20 g/m^2 infused after 6 hours of cisplatin has been well tolerated with little compromise in oncologic outcome. STS can reduce toxicities from cisplatin by quenching reactive oxygen species, preserving the activity of antioxidant enzymes, and forming biologically inactive complexes with cisplatin to effectively reduce the systemic exposure to cisplatin. In pediatric hepatoblastoma study, STS 20 g/m^2 was given after cisplatin 80mg/m^2. For lower dose, weekly cisplatin, 10g/m^2 would be reasonable, as only half dose of cisplatin (40mg/m^2) is given. In animal studies, STS given 4 hours after cisplatin was able to protect rats from ototoxicity with minimal compromise in anti-tumor activity of cisplatin, whereas STS 8 and 12 hours after cisplatin had less and no protective effects at all [13]. STS is a FDA approved agent for treatment of cyanide poisoning and it is approved to be given as a single dose of 12.5g after infusion of 300mg of sodium nitrite. In a phase 3 trial for calciphylaxis, STS is given 25 g per day for 3 times a week[14].

## 2 Study Objectives

### 2.1 Hypothesis

We hypothesize that use of intravenous STS would be feasible in patients with locally advanced SCCHN undergoing concurrent chemoradiation with cisplatin.

### 2.2 Primary Objective and Endpoint

Primary Objective	Endpoint	Time Frame
To establish feasibility of intravenous STS after each dose of concurrent cisplatin in patients with locally advanced head and neck squamous cell carcinoma undergoing definitive radiotherapy.	Feasibility measured by successful completion of planned treatment, defined by completion of at least 5 weekly cisplatin or 2 high dose cisplatin administrations without extended treatment related delays more than 7 days.	Occurring up to 7 days after the last dose of STS

[figure not shown]

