## 3 Study Design

### 3.1 Characteristics

This is a phase II study to determine feasibility of STS infused 4 hours after each dose of either weekly or every-3-week cisplatin in SCCHN patients undergoing definitive concurrent chemoradiation with cisplatin. Patients with locally advanced SCCHN (oral cavity, oropharynx, hypopharynx, and larynx) eligible for definitive concurrent chemoradiation with cisplatin would be eligible for the study.

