### 3.2 Sample Size

Target accrual is a total of 16 patients, and to account for screen failures and withdrawals, we will consent up to 18 patients. Patients can be enrolled to the and can get concurrent chemoradiation with weekly cisplatin (40 mg/m^2) given once a week or concurrent chemoradiation with high dose cisplatin (80-100 mg/m^2) given every 3 weeks. Participants who do not receive any dose of STS will not be evaluable and will be replaced.

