### 5.2.5 Switching to weekly cisplatin from every-3-week cisplatin

If a participant experiences any of the above adverse events requiring dose modification, every-3-week cisplatin can be switched to weekly cisplatin at least 3 weeks after the first dose of every-3-week cisplatin, at the treating physician's discretion. All adverse events should be resolved to baseline or CTCAE grade  $\leq 1$  before weekly cisplatin can be resumed. If the switching happens, the participant can continue STS infusion at 10mg/m^2 as outline in section 5.1.

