## **8 Statistical Considerations and Analysis Plan**

Feasibility will be evaluated as the successful completion of 5 weekly cisplatin or 2 every-3-week cisplatin without any extended treatment related delays more than 7 days by at least 75% of patients. Safety will be measured by:

- Frequency of drug related adverse events occurring up to 7 days after the last dose of STS
- Frequency of serious adverse events occurring up to 7 days after the last dose of STS
- Frequency of clinical laboratory test abnormalities by worst toxicity grade using NCI CTCAE version 5.0

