## 8.4 Analyses Plans

We will report the proportion of patients experiencing high-grade toxicity with exact binomial 95% confidence intervals. We will also describe patient experiences with respect to feasibility as defined above. All other adverse events will be similarly summarized by type and grade.

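### The STS feasibility rule counts only cisplatin doses and delays, so STS infusions omitted while cisplatin continues do not count against feasibility

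*Combined protocol and SAP*

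**What the plan says.** Section 2.2 states the objective as feasibility of intravenous STS following every cisplatin dose. Section 3.1 agrees: "This is a phase II study to determine feasibility of STS infused 4 hours after each dose of either weekly or every-3-week cisplatin".

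The success rule appears in three places.
- Section 2.2: "Feasibility measured by successful completion of planned treatment, defined by completion of at least 5 weekly cisplatin or 2 high dose cisplatin administrations", with no treatment-related delay over 7 days. The time frame is "Occurring up to 7 days after the last dose of STS".
- Abstract: "Feasibility will be assessed by successful completion of planned treatment, defined by completion of 5 weekly cisplatin or 2 high dose cisplatin", with the same delay condition.
- Section 8: "Feasibility will be evaluated as the successful completion of 5 weekly cisplatin or 2 every-3-week cisplatin", with the same delay condition, to be met by at least 75% of patients.

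Section 8.4 adds: "We will also describe patient experiences with respect to feasibility as defined above".

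On STS delivery itself, the footnote to Table 5.1 says that missed STS doses are not made up. Section 5.2.5 says of patients moved to weekly cisplatin: "If the switching happens, the participant can continue STS infusion". Section 3.2 says: "Participants who do not receive any dose of STS will not be evaluable and will be replaced".

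**The concern.** The objective concerns whether STS can be given after each cisplatin dose. The rule asks whether cisplatin could be completed on time in patients who had at least one STS infusion. These questions overlap, because STS toxicity that stops cisplatin or delays it by more than 7 days counts as failure. They part when an STS infusion is left out (for reasons of access, timing, tolerance or refusal, say) and cisplatin goes ahead. That patient still succeeds.

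Omitting STS also removes the exposure whose effect on cisplatin the rule is meant to test, so a high completion rate could coexist with little STS. Section 1.3 makes a larger study depend on STS infusion looking feasible and safe here, and the plan supplies no delivery figure for that judgement.

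**Working it through.** **1. What each planned measure counts.**

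| Place | Measure | STS delivery? |
|---|---|---|
| Abstract, 2.2, 8 | Cisplatin doses (5 weekly or 2 every 3 weeks); delays over 7 days | No |
| 2.3 | Hearing, tinnitus, PRO-CTCAE, HHIA-S | No |
| 5.4, Table 1 | Cumulative cisplatin of 200 mg/m² | No |
| 8, safety | Adverse events, serious adverse events, laboratory grades | No |
| 8.4 | High-grade toxicity with exact CI; feasibility as already defined | No |

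The plan's only feasibility threshold is 75%, or 0.75 × 16 = 12 patients, on the cisplatin rule. It gives no STS-delivery figure to reproduce.

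**2. Floor per patient.** Section 3.2 makes a patient evaluable after one STS infusion. The cisplatin criterion is met with 5 to 7 weekly or 2 to 3 every-3-week doses. The least STS compatible with success under the Abstract and Section 8 is 1/5 = 20% to 1/7 = 14% (weekly) and 1/2 = 50% to 1/3 = 33% (every 3 weeks). This is a logical limit, not a forecast.

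**3. Illustration.** Let q be the share of infusions omitted while cisplatin continues, and m the infusions due. Both q and the within-patient correlation are assumptions.
- Independent omissions: P(all given) = (1−q)^m.
- Correlation 0.3 (beta-binomial): P(all given) = product over k = 0,…,m−1 of (b+k)/(s+k), with s = 0.7/0.3 = 2.333 and b = (1−q)s.

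| m | q = 5% (indep. / 0.3) | q = 10% | q = 20% |
|---|---|---|---|
| 2 | 0.902 / 0.917 | 0.810 / 0.837 | 0.640 / 0.688 |
| 3 | 0.857 / 0.892 | 0.729 / 0.792 | 0.512 / 0.614 |
| 5 | 0.774 / 0.856 | 0.590 / 0.729 | 0.328 / 0.519 |
| 7 | 0.698 / 0.831 | 0.478 / 0.686 | 0.210 / 0.459 |

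Expected patients with at least one missed infusion = 16 × (1 − P). Over all schedule splits, the smallest value comes from m = 2 with correlation 0.3 and the largest from m = 7 with independence:
- q = 5%: 1.33 to 4.83, about 1–5
- q = 10%: 2.61 to 8.35, about 3–8
- q = 20%: 4.99 to 12.64, about 5–13

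These are not conditioned on having had at least one infusion. For m = 2 with correlation 0.3, both are omitted with probability q(q + 0.3(1−q)) = 0.017, 0.037 or 0.088. Conditioning lowers the lower ends to about 1, 2 and 4 (for example 16 × (0.312 − 0.088)/0.912 = 3.9). The upper ends do not change.

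**4. The time frame in 2.2.** Suppose it were read literally as a cut-off at last STS day + 7, on nominal days.
- Weekly: last STS on day 1, 8, 15 or 22 closes the window on day 8, 15, 22 or 29, with 2, 3, 4 or 5 cisplatin doses inside.
- Every 3 weeks: last STS on day 1 or 22 closes it on day 8 or 29, with 1 or 2 doses inside.
- With a skipped dose (cisplatin on days 1, 8, 15, 22 and 36, last STS on day 22), it closes on day 29 with four doses.

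So a literal cut-off can fall before the cisplatin count is complete. It still sets no requirement on how many STS infusions were given.

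**5. Precision of an added measure.** Clopper-Pearson 95%: 14/16 gives 61.7–98.4%; 7/8 in one schedule (8 patients assumed) gives 47.3–99.7%. For a rate over infusions, with 5 per patient and correlation 0.3, the design effect is 1 + 4 × 0.3 = 2.2. A binomial interval on infusions would be too narrow by √2.2 = 1.48.

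**6. If the team chose an STS threshold.** Assume 85% cisplatin completion: P(at least 12 of 16) = 0.921. An STS bar of 12 or 14 of 16 is met with probability 0.983 or 0.789 if 90% of patients receive every infusion, and 0.798 or 0.352 if 80% do. Multiplying by 0.921 (independence) gives 0.905 or 0.727, and 0.735 or 0.324.

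**The case against.** The best defence is that the rule tests the question that matters most clinically: whether adding STS compromises cisplatin. That is a legitimate part of feasibility, and the criterion should stay. It does not show that STS could be given after each dose.

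Other points have force. Section 8.2 seeks only preliminary evidence and Section 8.4 is descriptive, so reporting STS delivery closes the gap without a second decision bar. The wording in 5.2.5 may be simple permission. The reasons for ending treatment in 3.5 include unacceptable adverse events and significant non-compliance, which may cover some omissions. Only the Table 5.1 footnote clearly foresees missed STS. A measure requiring every infusion is stricter than a cisplatin rule that accepts 5 of 7 or 2 of 3.

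A reader might also infer more than the documents support:
- That many infusions will be missed. No omission rate is given.
- That STS data will not exist. STS is on the study calendar at each treatment visit, treatment is recorded on CRFs (9.6), and results are discussed monthly (Appendix 2). What is missing is their use.
- That 2.2 and Section 8 plainly score patients differently. The time frame matches the adverse-event wording in Section 8 and reads best as an observation window.
- That the two readings always agree once STS is given on day 22 or later. The skipped-dose example shows they need not.

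**Conclusion.** The point holds as a gap between the objective and the measure, and should be fixed. It rests on the text: the rule in the Abstract, 2.2 and Section 8 has no STS component, nothing else planned supplies one, and participants who receive no STS leave the denominator. The floor of 1 in 5–7 or 1 in 2–3 infusions follows from the Abstract and Section 8 alone. The counts of 1–5, 3–8 and 5–13 of 16 depend on assumed omission rates, independence or a correlation of 0.3, and 5–7 weekly or 2–3 every-3-week doses. They show how far delivery could fall unseen, not what is expected. The time frame does not close the gap and needs only clarification. The documents do not require a formal STS threshold.

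**What to change.** In the Abstract, 2.2 and Section 8:

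- Keep the cisplatin criterion. Add a pre-specified, co-reported measure: the proportion of evaluable patients who received STS after every cisplatin dose they were given, within the protocol's timing window. Give an exact 95% CI, overall and by starting cisplatin schedule.
- Report the share of planned infusions given descriptively, because infusions cluster within patients. This also shows partial delivery that the all-doses measure hides.
- Report how many participants started cisplatin on study but received no STS, with reasons, so that replacement under 3.2 does not hide delivery failures.
- Reword the 2.2 time frame to cover the whole cisplatin course, even if STS stops earlier.
- Reconcile the STS timing in the Abstract, 1.4 and 3.1 (4 hours) with Table 5.1 (4–5 hours), so that one window applies.
- State any conclusion that STS is feasible alongside the delivery result. Whether to add a formal STS threshold is for the team to decide in advance.

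The cost is endpoint wording, one tabulation, and capture of STS start times if they are not already recorded. Intervals will be wide at n=16, and the feasibility statement may be less favourable. If a threshold is chosen, the chance of concluding feasibility also falls, slightly or a great deal depending on the bar (step 6 of the working).
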